Study Protocol

Official Title: Using Data-Driven Implementation Strategies to Improve the Quality of Cirrhosis Care

ClinicalTrials.gov ID (NCT number): NCT04178096

Protocol Date: September 9, 2021

Scientific Background

Cirrhosis, or advanced liver disease, affects approximately four million people in the US. Approximately 100,000 Veterans under the care of the Veterans Health Administration (VA) have cirrhosis due to alcohol, hepatitis C (HCV), fatty liver disease, or other causes, and this number is rapidly increasing. There are lifesaving measures that providers can take to prevent harm from cirrhosis, including providing access to screening for liver cancer. However, less than 30% of Veterans receive guideline-concordant cirrhosis care.

In 2015, the VA's HIV, Hepatitis and Related Conditions Program Office (HHRC) established the national Hepatic Innovation Team (HIT) Learning Collaborative as part of its efforts to improve Veterans' access to new, highly effective HCV treatments. The PI's previous work evaluating the HIT Collaborative program identified specific implementation strategies that were associated with higher rates of HCV treatment using an annual 73-item survey based on the Expert Recommendations for Implementing Change (ERIC) implementation strategy taxonomy.

In 2018, the HIT Collaborative's focus pivoted from HCV elimination towards cirrhosis care. The PI's evaluation team and other investigators aimed to develop a manualized cirrhosis care intervention that would help VA facilities develop and roll-out implementation strategies unique to their needs. The framework for this manualized intervention was based on an implementation strategy bundle called Getting To Outcomes (GTO), a 10-step approach that guides organizations through the process of choosing, implementing, evaluating, and improving an evidence-based practice (EBP) or intervention. While GTO had been applied to many content domains and settings, it had yet to be tested in healthcare settings. In addition, GTO was designed for selection of effective *interventions*, not for the selection of *implementation strategies* to implement a pre-specified intervention.

Thus, "Getting to Implementation" (GTI) was created to support the selection, tailoring, and use of implementation strategies in health care settings. An adaptation of GTO, GTI was developed using the evaluation team's surveys to identify effective strategies associated with improved cirrhosis care, as well as interviews with providers at VA facilities that were performing well on guideline-concordant cirrhosis care metrics.

This study aims to test the effectiveness of GTI to increase cirrhosis EBP uptake in VA facilities that are performing low on cirrhosis care metrics.

Study Objectives

The goal of this study is to assess the effectiveness of GTI's set of prescribed data-driven implementation strategies in increasing liver cancer screening for Veterans with cirrhosis at participating VA facilities. GTI is an 8-step program supported by a facilitation team with clinical and evaluation expertise that provides participating facilities' implementation teams with guidance and training to select and implement effective strategies to best fit their needs in order to improve care.

Study Design & Methods

This interventional study is a hybrid type III, stepped-wedge, cluster-randomized trial. Participating facilities will be randomized to the time that they receive the intervention. All intervention activities will be completed virtually.

Study Procedures

Intervention

Getting to Implementation (GTI) is an 8-step intervention involving biweekly meetings with a 2-person facilitation team. In addition to the participating facility's preliminary step of forming a local implementation team, GTI steps include:

- Step 1 – Identify Gaps and Goals
- Step 2 – Assess Facilitators and Barriers
- Step 3 – Choose Implementation Strategies
- Step 4 – Adapt Strategies and Address Readiness
- Step 5 – Plan Implementation
- Step 6 – Implement and Evaluate
- Step 7 – Improve Implementation
- Step 8 – Sustain Implementation

The intervention is delivered to the participating facility's implementation team over a 6-month active implementation period, followed by a 6-month sustainment period.

Manual

The GTI manual will guide the intervention. It includes step-by-step instructions through the GTI steps, worksheets, and resources. The GTI manual specifies eight “core” strategies found to be empirically associated with better cirrhosis care outcomes. Each of the core implementation strategies includes an accompanying appendix to aid in operationalizing it, and a tracking form to document use and fidelity.

Meetings

GTI facilitators will hold biweekly, 1-hour virtual meetings for a 6-month period to guide the participating facility's implementation team through GTI. This will be followed by 3 additional meetings over the 6-month sustainment period.

Toolkit

The GTI Toolkit includes editable versions of worksheets from the GTI manual. Participating facilities will complete these tools collaboratively with facilitators during meetings.

Data Collection

Facilitators will track GTI implementation and fidelity from several sources. A tracking spreadsheet will be used to record the time spent on each step, how and by whom GTI tools were completed, challenges encountered, and other relevant field notes. Additional sources include contemporaneous notes from biweekly meetings; completed GTI tools; and summative interviews with local implementation teams asking about their experiences with GTI and facilitation, the core strategies, and barriers and facilitators experienced.

Clinical outcomes at the facility- and patient-level will be obtained from the national Advanced Liver Disease Dashboard, which uses data from the VA's Corporate Data Warehouse (CDW) to identify Veterans with cirrhosis and to track interventions such as abdominal imaging (i.e., liver cancer screening).

Study Population

VA Facilities

We will enroll up to 12 VA facilities in the lowest quartile of guideline-concordant cirrhosis care. Implementation will be conducted in three steps over a 2-year period, with four facilities crossing from control to intervention every 6 months until all sites are exposed to the intervention.

Veterans

Veterans with cirrhosis engaged in care at a participating VA facility will be included in analysis. Engagement in care will be defined as having at least one encounter for clinical care in the prior 18 months. Veterans will be assigned to the facility in which they receive their primary care at the time of randomization.

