Study Statistical Analysis Plan (SAP)

Official Title: Using Data-Driven Implementation Strategies to Improve the Quality of Cirrhosis Care

ClinicalTrials.gov ID (NCT number): NCT04178096

Document Date: December 30, 2024

Statistical Analysis Plan

Data were analyzed using intent-to-treat principles, such that Veterans were assigned to their Veterans Health Administration (VA) facilities at the start of the study and all VA facilities were included in analysis (other than those no longer part of the VA Corporate Data Warehouse due to change to the Cerner electronic health record mid-trial). The primary question was whether GTI was associated with improved hepatocellular carcinoma (HCC) surveillance rates at the end of intervention and at 12 months post intervention. This was assessed using generalized linear mixed models with logistic regression. Investigators first modeled the association between Getting to Implementation (GTI) and HCC surveillance without adjustment for individual- or facility/cluster-level covariates. Subsequently, they adjusted for individual- and cluster-level covariates, and then did sensitivity analyses to assess whether removing early pandemic period (January 1, 2020–September 30, 2020) data impacted models. These models all assessed the patient-level binary outcome of receipt of HCC surveillance in the 6-month period. Initially, investigators specified three random effects: the random effect for the repeated measures from individual i in cluster k , the random cluster-by-time interaction, and the within-cluster ICC. However, the cluster-by-time interaction was found to be unneeded because it approximated 0. Note that the assignment of interventions is confounded with time in the stepped-wedge, cluster-randomized trials, so modeling the background secular trend is important to remove the bias in estimating the effect attributed solely to the intervention. Investigators assume that the average secular trend is a distinct value during each period, and they used a nonparametric representation for the time effect (categorical time).

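### Do the population and outcome rules count Veterans with liver cancer or a transplant as surveilled, and keep those who die in the denominator?

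*Protocol*

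**What the plan says.** Under Study Population, Veterans, the Protocol states that "Veterans with cirrhosis engaged in care at a participating VA facility will be included in analysis". It then adds that "Engagement in care will be defined as having at least one encounter for clinical care in the prior 18 months", and that "Veterans will be assigned to the facility in which they receive their primary care at the time of randomization". It does not give the date from which the 18 months are counted back.

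Under Data Collection, the Protocol takes outcomes from the national Advanced Liver Disease Dashboard, which is said to identify Veterans with cirrhosis and to "track interventions such as abdominal imaging (i.e., liver cancer screening". The dashboard's own inclusion and outcome logic is not reproduced.

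The SAP describes the endpoint as the "patient-level binary outcome of receipt of HCC surveillance in the 6-month period". It explains intent-to-treat by saying that "Veterans were assigned to their Veterans Health Administration (VA) facilities at the start of the study" and that all facilities were analysed, apart from those that left the data warehouse with the change of health record system. Time enters the model as a categorical effect.

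Neither document lists the qualifying imaging modality or indication. Neither mentions prior HCC, incident HCC, liver transplant or death.

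**The concern.** Surveillance means looking for cancer in people not known to have it. If a Veteran with known HCC or a transplanted liver stays in the cohort, diagnostic or follow-up scans could be scored as success. If the cohort is fixed at randomisation and no exit rule applies, a Veteran who dies could be scored as not surveilled in every later period. If engagement is instead re-assessed each period, a Veteran who died soon after a visit could still meet the 18-month rule for up to 18/6 = 3 further periods, and an imaging visit might itself create eligibility.

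At stake are the reported surveillance rates and the size of the Getting to Implementation (GTI) effect. The SAP asks about two time points, the end of intervention and 12 months later. If deaths were retained, the later point would carry the larger dead share, so a sustained effect could look like one that fades. Cirrhosis carries real mortality, so the question deserves a check.

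**Working it through.** The plan gives no event rate, mortality, effect size or power figure on this point, so there is nothing to reproduce. The check has two parts: what the text commits the analysts to, and how large the effect would be under the unfavourable reading.

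**Part 1: the text**

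- *Imaging.* The Data Collection sentence describes a data source in passing, and its gloss points towards screening. It does not say that any abdominal scan counts. The SAP then names the endpoint as HCC surveillance.
- *Death.* Intent-to-treat in the SAP is spelled out as facility assignment at study start and inclusion of facilities. It does not say that person-periods after death are scored as failures. A mixed model accepts unequal numbers of records per person, so a Veteran's records can simply end.
- *Re-assessment.* Fixing at the start is stated in both documents, though for facility rather than for engagement. Period-by-period re-assessment is stated in neither. Even if it were done, a look-back from the start of a period cannot make imaging within that period the source of eligibility for it. It could only carry eligibility into later periods.

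So at least one natural reading, a cohort fixed at the start with records ending at death or HCC, gives a sound denominator.

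**Part 2: size if such Veterans were retained**

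Assumed inputs:

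- True rates among eligible Veterans of 30% (control) and 40% (GTI). The nearest document figure is the Protocol's background statement of less than 30%, which concerns cirrhosis care generally.
- Annual mortality *q* of 5-15%.
- HCC or transplant share *h* of 2-8%, with 90% of them imaged under both conditions.
- Horizons of 18 and 36 months. The latter is the 12-month endpoint of the last step if it crosses at month 18: 18 + 6 + 12 = 36.

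Formulas:

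- Dead share D = 1 − (1 − q)^t.
- Observed rate = (1 − D) × [(1 − h) × p + h × 0.90].
- Odds ratios are marginal, so they only approximate what the SAP's conditional model would give.

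| Scenario | D | Observed rates | Difference (points) | Odds ratio |
|---|---|---|---|---|
| Ineligible removed | 0 | 30.0% vs 40.0% | 10.0 | 1.56 |
| q = 5%, 18 months, h = 0 | 7.4% | 27.8% vs 37.0% | 9.3 | 1.53 |
| q = 15%, 18 months, h = 0 | 21.6% | 23.5% vs 31.3% | 7.8 | 1.49 |
| q = 5%, 36 months, h = 0 | 14.3% | 25.7% vs 34.3% | 8.6 | 1.51 |
| q = 15%, 36 months, h = 0 | 38.6% | 18.4% vs 24.6% | 6.1 | 1.44 |
| No deaths, h = 2% | 0 | 31.2% vs 41.0% | 9.8 | 1.53 |
| No deaths, h = 8% | 0 | 34.8% vs 44.0% | 9.2 | 1.47 |
| q = 15%, 36 months, h = 8% | 38.6% | 21.4% vs 27.0% | 5.6 | 1.36 |

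Worked example, fifth row: D = 1 − 0.85³ = 0.386; observed rates are 0.614 × 0.30 = 0.184 and 0.614 × 0.40 = 0.246; the difference is 6.1 points.

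A separate grid used deaths of 0-5% per six-month period over up to four periods, a share *h* of 0-10%, and imaging rates of 70% or 90% in that share. Its non-zero scenarios gave differences of 9.7 down to 7.3 points, with an odds ratio of 1.40 at the lowest. The direction never changes. The odds ratio, the scale on which the SAP models the effect, moves proportionately less than the difference.

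**The case for a change.** The strongest case for acting is that the silence is real: no stated patient-level rule removes these Veterans, and nothing suggests that text was blacked out here. The remedy looks cheap, since it needs only date-based programming on data already held. Categorical time does not answer the point completely either. It absorbs shifts in level common to all facilities in a period, but it does not restore an effect diluted by people who cannot respond.

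Most of that stands as description. The definition, the exit rule and the reference date are unwritten, and dilution would follow if the dead were scored as failures. What does not stand is the step from an unwritten rule to a wrong one. The documents do not show that these Veterans were miscounted, and the dashboard may already exclude them.

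Nor is the dilution a threat to validity in the usual sense. Facilities are randomised to their crossover time, so the shares with HCC, transplant or death should be similar in expectation within a period. What remains is mainly an understated effect. A false positive would need those shares to differ by facility, or GTI to change imaging that is not surveillance. Growth in both shares is also not assured, because Veterans with HCC die too.

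The suggested exclusions carry a risk of their own. Surveillance finds HCC. Dropping the period of diagnosis, or refusing to count a scan dated on the day of diagnosis, would delete genuine surveillance successes. If GTI increases screening and hence detection, more of these deletions would fall in intervention periods.

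**Conclusion.** No change to the plan follows. The documents leave three details unwritten: which imaging qualifies, the date from which the 18-month window runs, and how HCC, transplant and death end a Veteran's contribution. An analyst working to an endpoint named HCC surveillance would be expected to settle all three sensibly, and a sensible solution fits the text as it stands.

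The harm needs the unfavourable reading to be the one used. Even then it is attenuation. With 5-15% annual mortality alone, a 10-point gain would show as 9.3 to 7.8 points at 18 months and 8.6 to 6.1 at 36 months. With the highest assumed mortality and HCC share together, it would show as 5.6 points, with an odds ratio of 1.36 in place of 1.56. These figures rest wholly on assumed mortality, HCC share, imaging rate and effect size. They also assume similar shares across facilities and that every Veteran who has died is scored as unscreened. They do not support the statement that the outcome is not HCC surveillance; they show only that its definition cannot be verified from these two documents.

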Study Statistical Analysis Plan (SAP)

Official Title: Using Data-Driven Implementation Strategies to Improve the Quality of Cirrhosis Care

ClinicalTrials.gov ID (NCT number): NCT04178096

Document Date: December 30, 2024

Statistical Analysis Plan

Data were analyzed using intent-to-treat principles, such that Veterans were assigned to their Veterans Health Administration (VA) facilities at the start of the study and all VA facilities were included in analysis (other than those no longer part of the VA Corporate Data Warehouse due to change to the Cerner electronic health record mid-trial). The primary question was whether GTI was associated with improved hepatocellular carcinoma (HCC) surveillance rates at the end of intervention and at 12 months post intervention. This was assessed using generalized linear mixed models with logistic regression. Investigators first modeled the association between Getting to Implementation (GTI) and HCC surveillance without adjustment for individual- or facility/cluster-level covariates. Subsequently, they adjusted for individual- and cluster-level covariates, and then did sensitivity analyses to assess whether removing early pandemic period (January 1, 2020–September 30, 2020) data impacted models. These models all assessed the patient-level binary outcome of receipt of HCC surveillance in the 6-month period. Initially, investigators specified three random effects: the random effect for the repeated measures from individual i in cluster k , the random cluster-by-time interaction, and the within-cluster ICC. However, the cluster-by-time interaction was found to be unneeded because it approximated 0. Note that the assignment of interventions is confounded with time in the stepped-wedge, cluster-randomized trials, so modeling the background secular trend is important to remove the bias in estimating the effect attributed solely to the intervention. Investigators assume that the average secular trend is a distinct value during each period, and they used a nonparametric representation for the time effect (categorical time).

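### The SAP leaves out whole randomised facilities that moved to Cerner mid-trial, although its model could keep any retrievable periods from before the move

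*SAP*

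**What the plan says.** The SAP opens with "Data were analyzed using intent-to-treat principles". It explains that Veterans were kept with their starting facility and that every facility entered the analysis, "other than those no longer part of the VA Corporate Data Warehouse due to change to the Cerner electronic health record mid-trial". The exception is worded by facility, not by facility and period.

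The primary question concerns "surveillance rates at the end of intervention and at 12 months post intervention". The method is a logistic mixed model: "These models all assessed the patient-level binary outcome of receipt of HCC surveillance in the 6-month period". Time is categorical, and there are random effects for individual and facility; the facility-by-time term was dropped as close to zero. The one sensitivity analysis described is "sensitivity analyses to assess whether removing early pandemic period" data, that is, January to September 2020.

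The protocol (Study Design & Methods) makes the facility the randomised unit: "Participating facilities will be randomized to the time that they receive the intervention". Under Study Population, VA Facilities, it plans up to 12 facilities, four crossing over every 6 months: "Implementation will be conducted in three steps over a 2-year period". Under Data Collection, cohort and outcomes come from a national dashboard fed by the Corporate Data Warehouse (CDW).

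**The concern.** In a stepped-wedge trial with at most 12 clusters, each facility is a sizeable part of the randomised evidence. Removing one entirely because of a mid-trial change of record system departs from the usual meaning of intent-to-treat. It also discards any usable periods the facility contributed before the change.

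The model does not force this choice. A mixed model with a categorical period effect accepts facilities that are observed in only some periods, so a switching facility could contribute until its switch and be missing afterwards.

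What is at stake is precision, and the reader's ability to judge it. Neither document says how many facilities were left out, from which waves, when they switched, or whether their history was still extractable. No analysis shows what the exception does to the result. The cost could be nothing, or it could be recoverable information on a small number of clusters.

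**Working it through.** **No figure to reproduce.** The documents give no sample size calculation, power, effect size or intracluster correlation. The one count that can be checked agrees: 3 steps × 4 facilities = 12.

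**Inputs from the documents.** 12 facilities in waves of 4/4/4, crossing over at successive six-month periods; categorical period; facility effect.

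**Assumptions, not in the documents.** One or two switching facilities, in any wave, switching at any time; b = 1 to 3 periods with all facilities in control; f = 0 to 2 follow-up periods after the last wave's first intervention period; T = b + 3 + f, from 4 to 7; equal facility sizes; a linear approximation to the logistic model; and, at first, one constant GTI effect.

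**Formula.** With unit residual variance, Var(GTI effect) = 1/RSS. RSS is the residual sum of squares of the 0/1 GTI indicator after removing facility and period effects. For n complete facilities,

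RSS = Σx² − T·Σ(facility mean)² − n·Σ(period mean)² + nT·(overall mean)².

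**Worked case, b = 1, f = 0 (T = 4).**

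- All 12 facilities: 24 − 14 − 18.667 + 12 = 3.333; variance 0.300.
- One wave-1 facility dropped: 21 − 11.75 − 16.273 + 10.023 = 3.000; variance 0.333; ratio 1.111.
- One wave-2 facility dropped: 22 − 13 − 16.909 + 11 = 3.091; variance 0.324; ratio 1.078.
- Wave 3 mirrors wave 1: ratio 1.111.

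Full-design variances for T = 4, 5, 6, 7 are 0.300, 0.268, 0.250, 0.239.

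**Loss from dropping whole facilities, all layouts.**

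| Facilities dropped | Variance | Standard error |
|---|---|---|
| One | +6% to +12% | +3% to +6% |
| Two, same wave | +15% to +31% | +7% to +14% |
| Two, different waves | +19% to +25% | +9% to +12% |

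**Share of the one-facility loss recovered by keeping data from before the switch.** Recovery = (ratio dropped − ratio kept)/(ratio dropped − 1). For example, with T = 4, a wave-1 facility and two periods kept: (1.111 − 1.028)/(1.111 − 1) = 75%.

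| Data kept up to | Wave 1 | Wave 2 | Wave 3 |
|---|---|---|---|
| All-control periods only | 0% | 0% | 0% |
| One period past first crossover | 60-87% | 26-39% | 16-23% |
| Two periods past first crossover | 60-92% | 100% | 60-92% |

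The first row is zero because a facility seen only while all facilities are in control adds nothing about GTI beyond its own level.

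**Check with a random facility effect.** Generalised least squares on facility-period means, with an assumed facility-to-residual variance ratio of 0.5 to 10, gives +5.8% to +12.2% for one facility and +13.6% to +31.6% for two in one wave. All-control periods again recover 0%. One period past the first crossover recovers 16-87%, and two recover 62-100%.

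**Check with effects that vary by time since crossover.** The SAP asks about two time points, so separate effects were fitted for exposure periods 1, 2 and 3 or later (f = 2, T = 6 or 7). Period 1 stands for the active period and period 3 or later for the 12-month effect. Dropping one facility raises the variance by 8-11% and 3-14% respectively. Keeping one period past the first crossover recovers 19-84% of the first loss but only 8-32% of the second.

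**The case against.** The strongest reply is that the exclusion may have been forced. The SAP's stated reason is that these facilities had left the CDW, and the protocol draws both cohort and outcomes from that source. Nothing says their history could still be extracted. If it could not, there was no analysis choice to criticise. This stands as a condition on the remedy. It does not explain why the SAP is silent on the point.

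Second, even retrievable data help only if they run past the first wave's crossover, and the loss is small when one facility is affected. Both points stand. So does the weaker recovery for the 12-month question; the higher recovery figures belong to the constant-effect model.

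Third, the exception and its cause are given in the same sentence as the intent-to-treat label, and the cause does not appear related to outcome. That is fair: nothing is concealed and no bias has been shown. Disclosing the reason still leaves out the number, waves and dates, and does not justify discarding usable periods.

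Fourth, keeping truncated facilities brings a missing-at-random assumption and unequal follow-up, and the SAP is written in the past tense, so the remedy is a post hoc re-analysis. These are real costs. Reporting both analyses lets the reader see how much the choice matters.

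The exception might have been meant to remove only data from after a switch. If so, one clarifying sentence would settle the matter.

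**Conclusion.** The concern holds. As written, the SAP excepts whole randomised facilities from an analysis it calls intent-to-treat, its model does not require that, and no sensitivity analysis covers it.

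The size is modest and uncertain. One lost facility costs 3-6% on the standard error under a constant effect; two would cost 7-14%. The recoverable part runs from none to all of the one-facility loss, depending on wave, switch date and retrievability, which the documents do not give. For the 12-month effect, keeping a single period past the first crossover recovers at most about a third. These figures rest on the assumed layouts, equal facility sizes and a linear approximation. The conclusion is about avoidable loss of precision and incomplete reporting, not bias.

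**What to change.** Where CDW data from before the switch can be extracted, include each switching facility in its randomised wave for every complete six-month period before its switch. Treat later periods as missing, and report the GTI effect with and without these facilities. Where nothing can be retrieved, say so. In either case, state how many facilities were affected, their waves and their switch dates.

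The cost is one data extraction, if historical records and covariates survive, and a re-run of the existing models. The analysis would then assume that periods after a switch are missing at random. Follow-up would be unequal across facilities, and these facilities may contribute no 12-month outcomes. If the retained data stop before the first wave's crossover there is no gain in precision, and the benefit is clearer reporting alone.

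### The primary question names two times, but the SAP does not anchor the later one and describes no model term or contrast for either

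*SAP*

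**What the plan says.** The SAP is one paragraph in the past tense. It states the primary question as whether GTI was associated with improved HCC "surveillance rates at the end of intervention and at 12 months post intervention". On method it says: "This was assessed using generalized linear mixed models with logistic regression". On the exposure it says only: "Investigators first modeled the association between Getting to Implementation (GTI) and HCC surveillance without adjustment"; adjusted models and a pandemic sensitivity analysis follow. The outcome is binary per six-month period. Time enters as categorical calendar period: "Investigators assume that the average secular trend is a distinct value during each period". The random effects are for individual and cluster; a cluster-by-period term was dropped after being estimated near zero.

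The Protocol has no analysis section. Under Study Procedures it gives GTI six active months and then six sustainment months. Under Study Population it says: "We will enroll up to 12 VA facilities in the lowest quartile of guideline-concordant cirrhosis care", and: "Implementation will be conducted in three steps over a 2-year period, with four facilities crossing from control to intervention every 6 months". The SAP analyses all facilities "other than those no longer part of the VA Corporate Data Warehouse due to change to the Cerner electronic health record mid-trial". Neither document gives the number of periods analysed or the number of facilities left.

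**The concern.** A question posed at two times needs two estimates, or a stated assumption that one number serves for both. The SAP provides neither. The reader also cannot tell which data answer the later half of the question, because its starting point is not given.

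A changing effect is plausible from the design. Five planning steps come before the implementation step (Step 6), so the effect may build. Facilitation falls from biweekly meetings to three meetings in six months, so it may fade. If one on/off coefficient was reported and the effect does change, the 12-month half of the primary question is not answered, and the odds ratio could be taken as evidence of lasting benefit.

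**Working it through.** The documents give no sample size, power or effect size, so there is no stated figure to reproduce. The check has four parts.

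**1. Does any described component separate the two times?**
- Categorical period is a calendar effect shared by all waves. It models the secular trend, not time since crossover.
- The cluster-by-period term is a random effect. A value near zero is not a test of whether the GTI effect depends on exposure time.
- Covariates and the individual and cluster effects do not carry exposure time.

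So no described component does so.

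**2. Where does the later time fall?** Adding 12 months to three possible starting points, in months from crossover:
- crossover itself: 0 + 12 = 12, so window 6-12;
- end of the active phase: 6 + 12 = 18, so window 12-18;
- end of sustainment: 12 + 12 = 24, so window 18-24.

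The earlier time is open too: month 6 (end of active phase) or month 12 (end of sustainment).

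**3. What would a single on/off term estimate?** On/off coding is an assumption here. Take three equal waves and four six-month periods, with one period before the first crossover (layout assumed). In a linear model with facility and period effects, each cell's contribution is r = x - wave mean - period mean + overall mean, where x is 1 when exposed. The wave means are 9/12, 6/12 and 3/12, the period means 0, 4/12, 8/12 and 12/12, and the overall mean 6/12.

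| r in twelfths | Period 1 | Period 2 | Period 3 | Period 4 |
|---|---|---|---|---|
| Wave 1 (0,1,1,1) | -3 | 5 | 1 | -3 |
| Wave 2 (0,0,1,1) | 0 | -4 | 4 | 0 |
| Wave 3 (0,0,0,1) | 3 | -1 | -5 | 3 |

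The sum over exposed cells is (5+1-3) + (4+0) + 3 = 10. The weights are:
- months 0-6: (5+4+3)/10 = 1.2
- months 6-12: (1+0)/10 = 0.1
- months 12-18: -3/10 = -0.3

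They sum to 1. With a random facility intercept the same layout gives 1.13 to 1.20, 0.10 to 0.13 and -0.30 to -0.25.

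Illustrative log-odds effects for the three windows (assumed):
- constant 0.40: result 0.40, OR 1.49, correct at every time;
- fading 0.40, 0.20, 0: 1.2×0.40 + 0.1×0.20 - 0.3×0 = 0.50, OR 1.65, against true ORs of 1.22 in months 6-12 and 1.00 in months 12-18;
- building 0.20, 0.40, 0.60: 0.24 + 0.04 - 0.18 = 0.10, OR 1.11, against true ORs of 1.49 and 1.82.

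The layout was then varied over assumptions not in the documents: 2 to 4 facilities left in each wave (27 patterns), 1 to 6 baseline periods, and 3 to 6 periods from first crossover, so 27 × 6 × 4 = 648 layouts. Each was run under 61 variance settings (ICC 0.001 to 0.1, 50 to 1,000 Veterans per facility-period, 0 to 60% of residual variance persisting within a Veteran, plus the facility-intercept limit), giving 648 × 61 = 39,528 settings.

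| On/off weight | Months 0-6 | Months 6-12 | Month 12 onward, total |
|---|---|---|---|
| All settings, equal facility sizes | 0.70 to 1.25 | 0.00 to 0.50 | -0.50 to -0.02 |
| 12 facilities, 4-6 baseline periods | 0.79 to 0.95 | 0.18 to 0.31 | -0.23 to -0.03 |
| Unequal facility sizes | 0.68 to 1.28 | -0.13 to 0.69 | -0.59 to -0.05 |

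Over linear and logistic checks together, a constant OR of 1.5 gives 1.50. An OR fading through 1.5, 1.22 and 1.0 gives 1.42 to 1.70. An OR of 1.2 rising to 1.5 gives 1.12 to 1.29.

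**4. Can the two times be separated?** With one GTI term per six-month exposure window plus categorical period, the design was full rank in every setting. Concurrent control is thinner. Counting from the first crossover, waves cross at months 0, 6 and 12, so the last unexposed wave is gone at month 12. For exposure months 0-6, waves 1 and 2 have an unexposed comparator; for months 6-12, only wave 1; beyond month 12, none.

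**The case against.** No analysis error is shown. The SAP is a brief retrospective summary and names both times before saying how the question was assessed. Its wording is compatible with phase terms in the model. If such terms were used, only the write-up is deficient. This stands, and it is why the bias figures are conditional.

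The force of the figures also depends on the anchor. If the later time means months 6-12, the negative weights fall on no named time and one wave still has a concurrent comparator. This stands too. But a weight of 0.00 to 0.50 on that window still means that an on/off coefficient is not that window's effect unless the effect is constant. If the earlier time is month 6, the on/off term puts most of its weight there, so the difficulty lies mainly with the later time.

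A changing effect is plausible but not demonstrated: the documents report no estimates.

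Three stronger readings are tempting and are not supported. A reader might infer that GTI was coded on/off and that a 12-month result is therefore wrong; the coding is not stated. A reader might infer from the plural models that a separate model was fitted to the later window alone; none is described. A reader might infer that the two-year period leaves no room for the later time; the Protocol applies it to implementation, not to outcome follow-up from routine data.

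**Conclusion.** The point holds as a gap in the plan. The primary question has two times, the later one is not tied to crossover, and the analysis as described gives no separate estimate at either. What was actually fitted cannot be determined.

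If GTI was a single on/off term and its effect changes, the coefficient mainly reflects the first six months of exposure, and the total weight on month 12 onward is negative. The exact weights rest on assumed layouts, on assumed variances and on a linear approximation, with a logistic check that gave similar odds ratios. Under a constant effect the on/off result is correct at both times. This should be fixed because it concerns half of the primary question. Confidence is medium because the coding is unknown.

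**What to change.** 1. Define both named times in months from crossover, and state how GTI was coded.
2. Estimate GTI with phase or six-month time-since-crossover terms in one model with categorical calendar period. Keep all exposure windows in that model and report one contrast per named time. If this was the model fitted, write out the terms and contrasts. If not, run it on the existing data, label it post hoc, and keep the on/off result beside it.
3. State the periods and the number of facilities contributing to each named time, after the electronic-record exclusion.
4. If the later time lies beyond month 12 from crossover, state that no concurrent unexposed facility exists there and that the estimate relies on additive period effects.

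The cost is wording only if phase terms were used, and otherwise one re-run. Precision falls. In the assumed settings, standard errors with six-month indicators are 1.01 to 1.26 times the on/off standard error for months 0-6, 1.27 to 1.88 for months 6-12, 1.54 to 2.56 for months 12-18 and 1.76 to 3.25 for months 18-24. The re-run does not create concurrent controls at the later time.
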